## **5.8. Study Drug Accountability**

The Investigator or designee will maintain accurate records of receipt and the condition of all study drugs including dates of receipt. In addition, accurate records will be kept by the pharmacist of when and how much study drug is dispensed and used by each patient in the study. Any reason for departure from the protocol dispensing regimen must also be recorded.

Patients/caregivers who have been trained to administer study drug at home between clinic visits will be dispensed an adequate supply of ALN-TTRSC. The number of vials dispensed to the patient will be recorded in the study drug accountability log. At each subsequent clinic visit, patients will be required to return all used and unused study drug vials to the site and the number of bottles will be recorded in the study drug accountability log by the site staff.

Drug accountability records and inventory will be available for verification by the Alnylam Monitor or designee. At the completion of the study, there will be a final reconciliation of all study drugs. Remaining study drug (all used, partially used, and unused vials) will be returned to Alnylam or its agent or destroyed at the site according to applicable regulations.

Study drug must not be used for any purpose other than the present study. Study drug which has been dispensed to a patient and returned unused must not be re-dispensed to a different patient.

Further instructions about study drug accountability are detailed in the ALN-TTRSC Pharmacy Manual.

## **5.9. Concomitant Medication / Treatment**

Use of any investigational agent other than tafamidis, diflunisal, doxycycline, or taurooursodeoxycholic acid, or an investigational device within 30 days prior to the first dose of study medication in this protocol is prohibited during study participation.

Medications and treatments other than those specified above, including palliative and supportive care approved by the Investigator for disease-related symptoms, are permitted during the study.

The Investigator should review over-the-counter (OTC) and or herbal preparations to ensure that these are not potentially disease modifying, and advise patients to limit heavy alcohol consumption.

Use of all concomitant medications from Screening/Baseline through the Follow-up visit will be recorded on the patient's CRF. This will include all prescription drugs, herbal preparations, OTC medications, vitamins, and minerals. Any changes in medications during the study will also be recorded on the CRF.

Any concomitant medication that is required for the patient's welfare may be given by the Investigator. However, it is the responsibility of the Investigator to ensure that details regarding the medication are recorded on the CRF. For coding of concomitant medication, an internationally recognized and accepted coding dictionary will be used.

## 6. STUDY ASSESSMENTS

Details of the timing of each assessment are presented in the Schedule of Assessments for Clinic Visits for Year 1 and Year 2 ([Table 1](#)), the Schedule of Assessments for Clinic Visits for Year 3 and Year 4 ([Table 2](#)), the Schedule of Assessments for Weekly Dosing Days Between Clinic Visits ([Table 3](#)), and the Pharmacokinetic Sampling Schedule ([Table 4](#)).

Screening/Baseline assessments may be performed during several clinic visits. If the final Day 90 visit in the ALN-TTRSC-002 study is within 28 days of the first dose administered in this study, then visit procedures performed as part of the Day 90 visit do not need to be repeated at the Screening/Baseline visit. If the Day 90 visit in the ALN-TTRSC-002 study occurred within 90 days of the first dose administered in this study, the echocardiogram and CMR do not need to be repeated at the Screening/Baseline visit. The results from samples collected predose are not needed prior to dosing.

The 14-day window for clinic visits applies to study assessments. Dosing is to maintain the weekly schedule ( $\pm$  2 days).

The End-of-study or ET visit is scheduled approximately 7 days following the last dose. The Follow-up visit is scheduled approximately 4 weeks following the End-of-study or ET visit, if applicable. Patients who discontinue early will be required to report to the clinic for an End-of-study visit and a Follow-up visit.

### 6.1. Demographic Data and Medical History

Patient demographic data will be obtained at Screening/Baseline. A complete medical history will be obtained at Screening/Baseline and will include past or present conditions of the following: general, head and neck, eyes, ears, nose and throat, chest/respiratory, heart/cardiovascular, gastrointestinal/liver, gynecological/urogenital, musculoskeletal/extremities, dermatological/skin, neurological/psychiatric, endocrine/metabolic, hematologic/lymphatic, allergies/drug sensitivities, past surgeries, substance abuse, or any other disease or disorder. The patient's HIV status will also be obtained.

Any AEs from the previous study (ALN-TTRSC-002) that are ongoing on Day 0 will be considered as part of the medical history and recorded as such on the CRF.

On Day 0 pre-dose, the medical history for each patient will be updated with any changes during the interval since the last recording. Any changes in medical history will be evaluated against the inclusion and exclusion criteria to determine the patient's continued eligibility for the study.

### 6.2. Karnofsky Performance Status

At the scheduled time points, each patient's Karnofsky Performance Status will be assessed before study drug dosing; see [Appendix 1](#) for a sample of the Karnofsky Scale.

### **6.3. Estimated Glomerular Filtration Rate**

Estimated glomerular filtration rate will be calculated using the MDRD formula. If this parameter met eligibility criteria at Screening/Baseline, then dosing can proceed prior to receiving pre-dose Day 0 results.

The formula is as follows:

$$\text{GFR (mL/min/1.73 m}^2\text{)} = 175 \times (\text{S}_{\text{cr}})^{-1.154} \times (\text{Age})^{-0.203} \times (0.742 \text{ if female}) \\ \times (1.212 \text{ if African American}) \text{ (conventional units)}$$

This formula estimates GFR using 4 variables (serum creatinine, age, ethnicity, and gender). For precision, the serum creatinine values should be in mg/dL to 2 decimal places (eg, 0.95 mg/dL) OR values in  $\mu\text{mol/L}$  to the nearest whole number (e.g., 84  $\mu\text{mol/L}$ ). The following eGFR calculator can be used to determine eGFR: <http://nkdep.nih.gov/lab-evaluation/gfr-calculators.shtml>.

### **6.4. Safety Assessments**

All safety assessment measures will be recorded in the patient's medical record and CRF.

#### **6.4.1. Physical Examination**

At the scheduled time points, physical examinations should be performed before study drug dosing and will include the examination of the following: general appearance, head, eyes, ears, nose and throat, chest/respiratory, heart/cardiovascular, gastrointestinal/liver, musculoskeletal/extremities, dermatological/skin, thyroid/neck, lymph nodes, and neurological/psychiatric.

#### **6.4.2. Body Weight and Height**

At the scheduled time points, body weight (measured in kilograms [kg]) will be obtained before study drug dosing; height will also be measured.

#### **6.4.3. Vital Signs**

At the scheduled time points, vital signs will be measured before study drug dosing. Vital sign measurements include blood pressure, pulse rate, oral body temperature, and respiratory rate. Vital signs will be measured manually in the supine position after the patient has rested comfortably for 10 minutes. Each patient's blood pressure should be taken using the same arm. Oral temperature will be obtained in degrees Celsius, heart rate will be counted for a full minute and recorded in beats per minute, and respirations will be counted for a full minute and recorded in breaths per minute.

Vital signs should also be collected during any unscheduled clinic visit, and before dosing at home, up to Day 84. For the safety of the patient, additional vital signs may be added at the discretion of the Investigator.

#### **6.4.4. Electrocardiogram**

At the scheduled time points, standard computerized 12-lead ECG recordings will be obtained in triplicate before study drug dosing. Each lead shall be recorded for at least 3

beats at a speed of 25 mm/sec. The electrocardiographic parameters assessed will be rhythm, ventricular rate, PR interval, QRS duration, QT interval, ST and T waves, and Bazett-corrected QT interval (QTcB).

The Investigator or designee is responsible for reviewing the ECGs to assess whether the results are within normal limits and to determine the clinical significance of the results. These assessments will be recorded on the CRF. For any clinically significant abnormal results (eg, ischemic ECG changes, wave/interval changes, or arrhythmia), the Investigator must contact the Medical Monitor to discuss continued participation of the patient in the study.

#### **6.4.5. Clinical Laboratory Tests**

At the scheduled time points, samples for clinical laboratory tests will be collected before study drug dosing. The following clinical laboratory tests will be performed by each study site's local laboratory or a central laboratory:

---

##### **Hematology**

---

- Hematocrit
- Hemoglobin
- Red blood cell (RBC) count
- White blood cell (WBC) count
- Mean corpuscular volume
- Mean corpuscular hemoglobin
- Mean corpuscular hemoglobin concentration
- Neutrophils, absolute and %
- Lymphocytes, absolute and %
- Monocytes, absolute and %
- Eosinophils, absolute and %
- Basophils, absolute and %
- Platelet count

---

##### **Serum Chemistry**

---

- Sodium
- Potassium
- Blood urea nitrogen (BUN)
- Creatinine
- Uric acid
- Lactate dehydrogenase (LDH)
- Glucose
- Phosphate
- Albumin
- Calcium
- Carbon dioxide
- Chloride

---

##### **Liver Function Tests**

---

- AST
- ALT
- Alkaline phosphatase (ALP)
- Bilirubin (total and direct)

---

##### **Coagulation Studies**

---

- Prothrombin time (PT)
- Activated partial thromboplastin time (aPTT)
- International normalized ratio (INR)

---

**Thyroid Function Test**

---

- Thyroid stimulating hormone (TSH)

---

**Serology Parameters**

---

- Hepatitis B surface antigens (HBsAg)
- Hepatitis B surface antibody (HBsAb)
- Anti-hepatitis C virus antibody (HCV Ab)

---

**Urinalysis**

---

- Visual inspection for appearance and color
- pH (dipstick)
- Specific gravity
- Ketones
- Protein
- Glucose
- Bilirubin
- Nitrite
- RBCs
- Urobilinogen
- Leukocytes
- Microscopy (if clinically indicated)

---

**Urine Pregnancy Testing (WOCBP only)**

---

- $\beta$ -human chorionic gonadotropin

---

Additional and repeat testing may be performed at the discretion of the Investigator.

In the event of an unexplained clinically relevant abnormal laboratory test occurring after study drug administration, the test should be repeated and followed up at the discretion of the Investigator until it has returned to the normal range or stabilized, and/or a diagnosis is made to adequately explain the abnormality.

**6.4.6. Pregnancy Test**

A serum pregnancy test should be performed at Screening/Baseline for WOCBP and a urine pregnancy test may be used at all other visits; urine pregnancy tests will be performed at the study site. Samples for the pregnancy test should be collected before study drug dosing. The results of the pregnancy test at Screening/Baseline must be known prior to administration of study drug. Patients who are pregnant are not eligible for study participation. Patients determined to be pregnant while on study will be followed until the pregnancy outcome is known (see Section 7.10).

**6.4.7. Eye Examination**

At the scheduled time points, an eye examination will be performed. These examinations will include assessment of visual acuity and slit-lamp evaluation and visual field, where possible. Visual acuity should be evaluated at the beginning of each specified visit in the study (ie, prior to slit-lamp examination). Visual acuity testing should be done with best (most recent) correction. Further details regarding the eye examinations will be provided in the Study Reference Manual.

#### **6.4.8. Concomitant Medications**

All medications the patient receives during the Screening/Baseline period through the Follow-up visit will be recorded. The indication for the medication must be assessed to determine if a new AE is present. After Day 84, the site should contact the patient by phone at least monthly to collect information on concomitant medications between clinic visits. See Section 5.9 for more details on prohibited and acceptable concomitant medications.

#### **6.4.9. Adverse Events**

Adverse events will be collected beginning with the first dose of study drug and through the Follow-up visit. After Day 84, the site should contact the patient by phone at least monthly to collect information on adverse events between clinic visits. See Section 7 for more details on the collection and reporting of AEs.

### **6.5. Pharmacodynamic Assessments**

Details of how samples will be collected, processed, and stored will be in the Study Laboratory Manual.

#### **6.5.1. Transthyretin**

At the scheduled time points, blood for serum total TTR levels will be collected before study drug dosing and assessed using an enzyme linked immunosorbent assay method.

#### **6.5.2. Vitamin A**

At the scheduled time points, blood for serum vitamin A levels will be collected before study drug dosing and analyzed at a central laboratory.

### **6.6. Pharmacokinetic Evaluations**

Blood samples for assessment of ALN-TTRSC concentration and possible metabolite analysis will be collected as noted in the Pharmacokinetic Sampling Schedule ([Table 4](#)). Please refer to the Study Laboratory Manual for details on the sample collection and processing for plasma PK samples.

### **6.7. Clinical Efficacy Assessments**

The clinical efficacy assessments are briefly described below. Further details on performing clinical efficacy assessments will be provided in the Study Reference Manual.

#### **6.7.1. Review of Cardiac Medical History and Treatment Changes**

Any changes to the patient's cardiac medical history and treatment regimen changes should be recorded. Changes to be documented may include, but are not limited to, onset or recurrence of atrial fibrillation, pacemaker placement, and change in diuretic regimen.

### **6.7.2. NT-proBNP, Troponin T, and Troponin I**

At the scheduled time points, blood samples for the quantification of troponin T, troponin I, and NT-proBNP (biomarkers of cardiac status) will be collected before study drug dosing. Quantification of these biomarkers will be performed at a central laboratory.

### **6.7.3. Echocardiography**

An echocardiogram with Doppler will be used for assessment of cardiac structure and function. Echocardiography will be performed. Details for image acquisition and upload for central review can be found in the Echocardiogram Site Instruction Manual.

### **6.7.4. Six-Minute Walk Test**

The 6-MWT will be performed to assess functional exercise capacity and will include pre- and post-walk assessment of O2 saturation, blood pressure, heart rate, and the Borg scale rating for dyspnea and fatigue. The Screening/Baseline assessment will include a practice and an actual 6-MWT test 1 hour apart; at subsequent visits the 6-MWT should be performed before study drug dosing. Attempts should be made to perform the test approximately the same time of the day during the visits.

The 6-MWT will be administered by staff trained in the protocol, as per the American Thoracic Society guidelines.

### **6.7.5. NYHA Classification**

NYHA classification will be recorded; the NYHA classification scale is provided in [Appendix 2](#).

### **6.7.6. Cardiac Magnetic Resonance Imaging**

Cardiac MRI with LGE will be performed on patients without contraindications (ie, pacemakers, severe renal failure with eGFR < 30 mL/min/1.73 m^2, defibrillators, or allergy to gadolinium).

Details for image acquisition and upload for central review can be found in the MRI Instruction Manual.

### **6.7.7. Modified Body Mass Index**

Assessment of nutritional status will be measured by the mBMI, which has been linked to autonomic dysfunction. Since the mBMI takes into account the serum albumin values along with body mass index (BMI; function of height and weight), it corrects for hypoalbuminemia and is considered more reflective of nutritional status than BMI alone.

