a Screening/Baseline assessments may be performed during several clinic visits. If the final Day 90 visit in the ALN-TTRSC-002 study is within 28 days of the first dose administered in this study, then visit procedures performed as part of the Day 90 visit do not need to be repeated at the Screening/Baseline visit. If the Day 90 visit in the ALN-TTRSC-002 study occurred within 90 days of the first dose administered in this study, the echocardiogram and CMR do not need to be repeated at the Screening/Baseline visit.

- b The results from samples collected predose are not needed prior to dosing.
- c The 14-day window applies to study assessments. Dosing is to maintain the weekly schedule ( $\pm$  2 days).
- d Refer to [Table 2](#) for the continued Schedule of Assessments in Years 3 and 4 and for the End-of-study or Early Termination (ET) visit. For patients who discontinue early and provide consent, overall health status will be documented by either telephone contact or non-patient contact follow-up (eg, medical record check) at time points corresponding to study Day 504 (Week 72), if applicable, and study Day 1344 (Week 192).
- e Prior to Screening/Baseline activities, the patient will sign and date an ICF. No study procedures should be performed prior to informed consent being obtained.
- f During the treatment period, doses will be administered weekly ( $\pm$  2 days). Doses may be administered and some assessments may be performed at the clinical site or at home according to Section 5.5.
- g Subcutaneous injection of ALN-TTRSC into the abdomen on Day 0 (after completion of all pre-dose evaluations and procedures) and then on subsequent days into other quadrants of the abdomen. The upper arm or thigh may also be used (see the ALN-TTRSC Pharmacy Manual). Dosing on Days 1, 2, 3, and 4 must be performed approximately 24  $\pm$  4 hours after the preceding dose of study drug.
- h On Day 0 pre-dose, only interval medical history will be collected. Changes in medical history during the treatment period will be captured as TEAEs or concomitant medication(s) as appropriate.
- i Serology tests include HBsAb, HBsAg, and anti-HCV Ab.
- j Assessment should be performed before dosing.
- k The pregnancy test will be performed for WOCBP only. A serum pregnancy test should be performed at Screening/Baseline. Urine pregnancy tests at other visits.

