**Table 2: Schedule of Assessments for Clinic Visits – Year 3 and Year 4**

Phase:	Treatment Period (Doses Administered Weekly between Visits a )							End of Study b	Follow-up b	
Study Year	Year 3				Year 4					
Study Week	Wk108	Wk120	Wk132	Wk 144	Wk156	Wk168	Wk180	Wk192	-	
Study Day:	756	840	924	1008	1092	1176	1260	1344/ET b	1372	
Window (days):	±14	±14	±14	±14	±14	±14	±14	±7	±14	
Procedure:										
Study Drug Administration c,d	X	X	X	X	X	X	X			
Pregnancy Test e,f		X		X		X		X		X
Karnofsky Performance Status e		X		X		X		X		X
eGFR e,g	X	X	X	X	X	X	X	X		X
Safety Assessments:										
Physical Examination e	X	X	X	X	X	X	X	X		X
Body Weight e		X		X		X				X
Vital Signs e,h	X	X	X	X	X	X	X	X		
12-Lead ECG e,i				X				X		
Serum Chemistry (including LFTs), Hematology, Urinalysis e	X	X	X	X	X	X	X	X		X
Coagulation e,j				X				X		X
TSH e				X				X		
Eye Examination				X				X		
Review Concomitant Medications	Continuous Monitoring									
Review/Record AEs	Continuous Monitoring									
PD Assessments:										
TTR e	X	X	X	X	X	X	X	X		X
Vitamin A e,k		X		X		X		X		X
PK Assessments										
Plasma PK Sampling l		X				X				

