b The End-of-study or ET visit is scheduled approximately 7 days following the last dose. The Follow-up visit is scheduled approximately 4 weeks following the End-of-study or ET visit, if applicable. Patients who discontinue early will be required to report to the clinic for an End of Study visit and a Follow-up visit. For patients who discontinue

early and have provided consent, overall health status will be documented by either telephone contact or non-patient contact follow-up (eg, medical record check) at time points corresponding to study Day 504 (Week 72), if applicable, and study Day 1344 (Week 192).

- c During the treatment period, doses will be administered weekly ( $\pm$  2 days). Doses may be administered at the clinical site or at home according to Section 5.5.
- d Subcutaneous injection of ALN-TTRSC into the abdomen. The upper arm or thigh may also be used (see the ALN-TTRSC Pharmacy Manual).
- e Assessment should be performed before dosing.
- f The pregnancy test will be performed for WOCBP only. A serum pregnancy test should be performed at Screening/Baseline. Urine pregnancy tests at other visits.
- g The serum creatinine values should be in mg/dL to 2 decimal places (e.g., 0.95 mg/dL) OR values in  $\mu$ mol/L to the nearest whole number (e.g., 84  $\mu$ mol/L) when calculating eGFR using the MDRD study equation; see <http://nkdep.nih.gov/lab-evaluation/gfr-calculators.shtml> for an eGFR calculator.
- h Vital sign measurements include blood pressure, pulse rate, oral body temperature, and respiratory rate. Vital signs will be measured manually in the supine position after the patient has rested comfortably for 10 minutes. Each patient's blood pressure should be taken using the same arm. Vital signs should be collected during any unscheduled clinic visit.
- i For the 12-Lead ECG, each lead shall be recorded for at least 3 beats at a speed of 25 mm/s. Triplicate recordings will be obtained. The electrophysiologic parameters assessed will be rhythm, ventricular rate, PR interval, QRS duration, QT interval, ST and T-waves and QTcB.
- j Coagulation studies include PT, aPTT, and INR and will be performed on all patients.
- k Blood samples for vitamin A will be analyzed by a central laboratory.
- l Refer to Table 4 for PK Sampling Schedule.

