#### **8.2.4. Clinical Activity Assessments**

Change from baseline by time point for 6-MWT will be summarized, where change from baseline is predose value (or final assessment from ALN-TTRSC-002, if a pre-dose assessment in this study is not required). Change from baseline will also be summarized where baseline is derived from predose assessments in ALN-TTRSC-002.

Frequency of hospitalization, cardiovascular hospitalization, and heart failure hospitalization will be summarized. All-cause mortality and cardiovascular mortality will be summarized using Kaplan-Meier curves.

Descriptive statistics will be presented for all clinical activity variables (NT-proBNP, troponin I, troponin T concentrations; selected echocardiography parameters; mBMI; NYHA classification; CMR imaging parameters). Patient reported QoL and disease burden will be assessed by summary statistics for the EQ-5D and KCCQ. Summary statistics will be provided for observed values and changes from baseline.

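### Table 2 schedules mBMI at Day 1344/ET but marks no body weight there, so the final or exit mBMI has a same-visit albumin and no scheduled same-visit weight

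*Protocol*

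**What the plan says.** Section 6.7.7 of the protocol defines mBMI by its components: "Since the mBMI takes into account the serum albumin values along with body mass index (BMI; function of height and weight"). Section 2.3 lists mBMI among the tertiary objectives. Section 8.2.4 includes it among the clinical activity variables, for which "Summary statistics will be provided for observed values and changes from baseline".

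Section 6.4.2 ties weighing to the schedule: "At the scheduled time points, body weight (measured in kilograms [kg]) will be obtained before study drug dosing; height will also be measured".

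In Table 2 (Years 3 and 4) the mBMI row is marked at Days 840, 1008, 1176 and 1344/ET, with no mark at Follow-up. The weight row has four marks, "Body Weight e X X X X", which fall at Days 840, 1008, 1176 and Follow-up (Day 1372). The pregnancy test row, on the same 24-weekly pattern, has five, "Pregnancy Test e,f X X X X X", at Days 840, 1008, 1176, 1344/ET and Follow-up.

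The timing of the last two visits is given in the Table 2 footnotes: "The End-of-study or ET visit is scheduled approximately 7 days following the last dose", and "The Follow-up visit is scheduled approximately 4 weeks following the End-of-study or ET visit, if applicable".

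Footnote d of Table 1 refers the reader to Table 2 "for the continued Schedule of Assessments in Years 3 and 4 and for the End-of-study or Early Termination (ET) visit". Section 4.4.2 likewise sends patients who withdraw to Table 2 for a complete ET visit. The 1344/ET column therefore serves early leavers from any year, as well as completers.

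**The concern.** A composite of albumin and BMI describes a patient at one moment only if its time-varying parts come from that moment. Adult height can be carried forward, but weight cannot be assumed constant in this population. These are patients with cardiac amyloidosis, and the protocol itself tracks changes in diuretic regimen as an outcome. Table 2 schedules the composite and its albumin at Day 1344/ET but not its weight, while weight is scheduled at Follow-up, where mBMI is not.

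The visit affected is the last mBMI of the study for completers and the exit mBMI for early leavers. If sites follow the marks literally, the value will either be missing or be put together from measurements on different dates. If some sites weigh the patient and others do not, the summary at this visit will mix same-visit weights with substitutes. The statistical analysis plan can choose which recorded weight to use, but it cannot recover one that was never taken. The same gap leaves the End-of-Study/ET safety visit without a scheduled weight.

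**Working it through.** The protocol gives no figure of its own to reproduce here. The check maps the marks in Table 2 to visits and then takes differences in study days.

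**Step 1: map the marks.**

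| Table 2 row | 840 | 1008 | 1176 | 1344/ET | Follow-up (1372) |
|---|---|---|---|---|---|
| mBMI | X | X | X | X | |
| Body weight | X | X | X | | X |
| Serum chemistry (includes albumin, section 6.4.5) | X | X | X | X | X |
| Pregnancy test | X | X | X | X | X |
| Karnofsky | X | X | X | X | X |
| Vitamin A | X | X | X | X | X |

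Chemistry is also marked at Days 756, 924, 1092 and 1260, which do not matter here. The mBMI visits without a weight are {840, 1008, 1176, 1344/ET} minus {840, 1008, 1176, Follow-up} = {1344/ET}. This is the only one in Table 2.

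**Step 2: check the column alignment.** As read from the PDF, the rows have ten cells for nine visits, with one blank cell between 1344/ET and Follow-up. Every row that carries a Follow-up mark (pregnancy test, Karnofsky, eGFR, physical examination, chemistry, coagulation, TTR, vitamin A) has it in the tenth cell and a separate mark in the eighth, the 1344/ET cell. The last weight mark is also in the tenth cell, and the eighth is empty.

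**Step 3: look for another source of weight at 1344/ET.** Physical examination (section 6.4.1) does not list weight, and neither do vital signs (section 6.4.3). Section 6.4.2 limits weight to the scheduled time points. No passage says which weight the Day 1344/ET mBMI should use.

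**Step 4: distance to the nearest scheduled weights, for completers.**

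- Previous weight: 1344 − 1176 = 168 days (24 weeks). With windows of ±14 days at Day 1176 and ±7 days at Day 1344, the range is (1344 − 7) − (1176 + 14) = 147 to (1344 + 7) − (1176 − 14) = 189 days.
- Next weight: 1372 − 1344 = 28 days after the visit.
- Relative to the last dose on Day 1337: the End-of-Study visit is 1344 − 1337 = 7 days after it, one ordinary dosing interval. Follow-up is 1372 − 1337 = 35 days after it.

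For an early leaver the age of the last scheduled weight depends on when treatment stops. Under the 24-weekly pattern of Table 2 it can reach about 24 weeks plus windows.

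**Step 5: sensitivity of mBMI to weight (illustration on assumed values).** The protocol gives neither a formula nor typical values. Assume mBMI = BMI × albumin in g/L, with 80 kg, 1.75 m and 40 g/L. Then 80 / 1.75² = 26.12, and 26.12 × 40 = 1045. With 77 kg, 77 / 1.75² = 25.14, and 25.14 × 40 = 1006. The difference is 39 units, or 3/80 = 3.75%. A mismatch of 1 to 5 kg gives 1/80 = 1.25% to 5/80 = 6.25%. This shows only that an error in weight passes through in proportion. It does not estimate how large the error would be.

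**Step 6: effect of the fix.** With weight marked at 1344/ET, the gap between weight and albumin at that visit falls from 168 or 28 days to 0.

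**The case against.** The best objection is that this rests on the position of one mark in a table read from PDF, in a region where the rows have one more cell than there are visits. Table 1, read the same way, is visibly misaligned, so its weight and mBMI rows are not relied on here. A single displaced mark in the weight row cannot be fully excluded. But all the other Follow-up marks in Table 2 fall in the same cell as the last weight mark, and each of those rows has a separate End-of-Study mark. The reading is therefore likely, though not certain.

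A second objection is that scheduling mBMI implies obtaining what it needs, and that section 6.7 leaves procedural detail to a Study Reference Manual not available here. That stands in part: a sensible site may weigh the patient. It removes the certainty of harm but not the inconsistency between the two rows, and it leaves the measurement to local initiative.

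A third is that the choice of which weight feeds a derived variable belongs in the analysis plan. That is true of the derivation rule but not of the measurement.

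Some stronger inferences are not supported:

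- *The final mBMI must be calculated from an old or an off-drug weight.* No text directs either substitute, and an unscheduled weight is possible. Off-drug would in any case describe only the Follow-up weight, because Day 1344 is one dosing interval after the last dose.
- *The last on-treatment weight change is lost.* Day 1176 supplies an on-treatment weight. What is missing is a scheduled weight at the End-of-Study/ET visit.
- *Early leavers are the patients whose weight is changing most.* That is plausible, but nothing in the protocol shows it.

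**Conclusion.** The point holds as an inconsistency in the schedule. Table 2 asks for mBMI at Day 1344/ET and draws the albumin there but schedules no weight, while sections 6.4.1 to 6.4.3 supply none. For completers the nearest scheduled weights are nominally 168 days before (147 to 189 at the window limits) or 28 days after, the latter about 35 days after the last dose. Up to all of the approximately 25 planned patients could be affected at this one visit.

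The consequence is modest. mBMI is one of many tertiary measures, it is summarised descriptively with no test or decision attached, and weight and mBMI marks coincide at the other Table 2 mBMI visits. The size of any error in mBMI cannot be derived from the protocol, since the 39-unit illustration depends on assumed values throughout. The conclusion rests on two conditions: that the Table 2 marks were read in their true columns, and that sites follow the schedule without adding an unscheduled weight. The correction is still worth making because a weight not taken cannot be recovered at analysis.

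**What to change.** Check the body weight row against the typeset Table 2. If the 1344/ET cell is indeed empty, reconcile the two rows by adding a body weight mark at Day 1344/ET. State in section 6.7.7 that mBMI at each visit uses the weight and albumin from that visit, so that the Follow-up weight is not used for the Day 1344/ET value. The existing Follow-up weight can stay as it is.

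The cost is one mark in a table, one sentence of text, and one weighing at a clinic visit where the patient is already examined and has blood drawn.
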